## Assessments

Participants' assessments will be conducted at baseline, 6, and 12 months of the intervention. The following table and cited references describe the surveys and measurements conducted at each time point:

Instrument	BL	6 mo	12 mo
Demographic, social support and potential mediators/moderators			
Demographic and socioeconomic status			
Demographic variables	X		
Socioeconomic status variables, use of nutrition assistance programs, environmental changes	X	X	X
Current medications	X	X	X
Social support provision, receipt and enjoyment			
Number of times a person completes a social support-related activity (SS provision)		X	X
Adapted Multidimensional Scale of Perceived Social Support Scale (MSPSS) – (SS perceived) 		X	X
Ratings each participant gives to the social support provided to them after they request support (SS perceived)		X	X
Total number of times other participants provided support to the individual (SS receipt)		X	X
EGameFlow (enjoyment) 		X	X
User engagement and user burden			
User Engagement Survey* (adaptation) 	X	X	X
User Burden Scale* (adaptation) 	X	X	X
Self-efficacy and -regulation and motivation			
Weight Efficacy Life-Style Questionnaire (WEL-Q) 	X	X	X
Treatment Self-Regulation Questionnaire (TSRQ) 	X	X	X
Potential drivers of weight loss			
NCI's Automated Self-Administered 24-hour Dietary Recall (ASA24®) – 3 unannounced recalls – two weekdays, one weekend day) 	X	X	X

Physical Activity (FitBit tracker) – minutes per week of MVPA (min:10h/d, 3 valid days) 	X	X	X
Exercise Vital Sign Questionnaire 	X	X	X
The Stanford Leisure-Time Activity Categorical Item (L-Cat), short version 	X	X	X
Physiological and anthropometric measures			
Height (self-report) / weight (FitBit Aria Scale) 	X	X	X
Hip and Waist circumference (self-report).	X	X	X
T2DM (Type 2 Diabetes Mellitus) risk factors (risk score 0 – 10)	X	X	X
Self-monitoring adherence and study compliance/responsiveness			
Monthly survey (self-monitoring)		X	X
Adherence to FitBit devices usage (mLife app – rewards or points)		X	X
Adherence to self-monitoring diet (mLife app - logging $\geq 2$ eating occasions per day)		X	X
Use of intervention components (mLife app - use of all intervention components)		X	X
Factors that may affect compliance: differential dropouts and reasons to discontinue the study		X	X
Factors that may affect compliance: assessment of major life events		X	X

18. ROSS, K. M.; WING, R. R. Concordance of In-Home "Smart" Scale Measurement with Body Weight Measured In-Person. *Obes Sci Pract*, v. 2, n. 2, p. 224-248, Jun 2016. ISSN 2055-2238. Disponível em: <<https://www.ncbi.nlm.nih.gov/pubmed/27499884>>.

Participants were informed about the timeframe for each assessment during the orientation session and two weeks before the 6- and 12-month assessments through emails and e-cards. At each assessment point, participants received detailed instructions for each component of the assessment.

The order of the assessment request was in all time points, dietary recalls, survey, physical activity and body weight. Protocols for each component of the assessment are described below.

## Dietary recalls

Dietary intake data (24-hour recalls) were collected and analyzed using the Automated SelfAdministered 24-hour (ASA24) Dietary Assessment Tool, version 2020 for cohort 1 and 2022 for cohort 2. Three unannounced dietary recalls were collected at each time-point. Invalid recalls (under 500kcals) were considered and participants were asked to complete another attempt. Total kcals for all valid recalls were averaged. A total of 5 weekdays and 5 weekend days are scheduled are each timepoints, thus enough makeup days are available for the

completion of the assessment.

### ***Steps to request a dietary recall***

1. Before the first recall date, the number of recalls completed and remaining per participant has to be determined. Data is exported from ASA24 research site “tracking feature”. If a participant has not enough recalls remaining (8 remaining at 6-mo assessment and 4 remaining at 12- mo assessment), a new account must be assigned by highlighting the participant in the ac- counts Excel database located in OneDrive/mLife/Assessment Materials/Cohort/Dietary re- calls and pasting their identifying information on the last account available.
2. Active participants in each cohort are identified at each assessment time-point (baseline and 12 weeks) by generating the “consort report” from RedCap. Desired participants are enrolled study participants, with a participant status “active” and who haven’t completed the required dietary recalls for that time-point.
3. All databases generated for tracking each recall are securely stored in an Assessment Materials OneDrive folder per cohort. A folder within the Dietary Recalls section is labeled with the date of each recall.
4. On the scheduled day, a recall request is emailed to the participant in the morning using Out- look mail merge, which pulls participant information from the active participants spreadsheet.
5. In the early afternoon of the recall date, a research assistant would examine the completion of the day using the ASA24 Researcher Site. They would then create a list of people to remind to complete the day’s recall on Excel utilizing the earlier created spreadsheet of participants who were contacted that day to complete a recall. The research assistant would then conduct re- minder phone calls using Google Voice. If not able to be reached by phone call, participants are texted. These contacts would be noted in the Reminder Call Excel Spreadsheet. After completing these phone calls, the research assistant would contact the faculty members asso- ciated with the recalls for the assessment time-point and update them on their contacts. The phone call and text message scripts are below.
6. Participants are required to complete the recall before midnight Eastern time zone on the day that the recall was requested in order to be considered completed and valid. In addition, each participant’s recall had a threshold of 500 kcal to be considered valid.
7. The following day, research coordinator imports to RedCap the kcal and date of the recall, and the participants who completed the prior day’s recall data.

## Survey

A single survey is requested for completion at each time point. Configure RedCap's Automated Survey Invitations (ASI) feature to automatically send the survey link to the participant's email. The customized email includes the unique survey link, a brief explanation of the survey's purpose, and deadlines for completing the survey at each time point. Set the system to send the initial survey invitation email to the participant immediately after they sign the informed consent form (baseline or on the date of the 6- or 12-month assessment launch). Schedule two reminder emails: the first will be sent **3 days after the initial invitation, and the second will be sent 7 days later.**

Participants are requested to provide self-reported anthropometric measurements, such as hip and waist circumference and body weight, and physiological measurements, like blood pressure, at each time point. These measurements are reported in the "measurements" section of the survey instrument. Detailed instructions are provided below.

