## Randomization Procedure

Participants were randomized to a gamified (*mLife+points*) or non-gamified (*mLife*) version of the *mLife* mobile weight loss intervention where provision of social support was incentivized by providing points for engaging in social support activities (for the *mLife+points* group) or not receiving points for social support activities (*mLife* group).

Participants are randomly assigned once 50% of the baseline assessments are completed (either the baseline survey or the three dietary recalls). A computerized blocks system, stratified by race (Black, Other) and sex, is used to ensure equal distribution among groups within each cohort. [name] generates a random list of two groups (0s = Standard, 1s = *mLife*) in blocks of 10 or 4. Separate blocks are created for women and men, as well as white and non-white participants, this results in 15 blocks of 10 for non-white women, 30 blocks of 10 for white women, 3 blocks of 5 for non-white men, and 5 blocks of 4 for white men.

As participants complete 50% of the assessment, a blind staff member uses the demographic data report from RedCap to identify each participant by gender and race and add the participant's ID number to the next available spot on the blocks. The group allocation will then be recorded in the RedCap project under the randomization form (randomization event). Participants will not be informed of their group assignment but will be provided with their choice of meeting times and days for the training session. On the day of randomization, participants will be contacted and asked to select the time and date they plan to attend. The group allocation will be revealed at the first group meeting, after all baseline assessments have been completed. Since the training sessions are scheduled by group, the randomization process must occur before inviting participants to the training meeting.

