### Hip and waist circumference

A tape measure is sent to the participants for hip and waist circumference measurements. The participant will be instructed to measure waist circumference at the iliac crest, and hip circumference will be measured at the maximum protuberance of the buttocks. Two measurements will be taken and should be within 4mm of one another. If they are not, a third measurement will be requested in the survey/

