#### Written tips:

- Stand up straight and breathe out. Use the tape provided for the study.
- Measure the distance around the smallest part of your waist, just above your belly button. This is your waist circumference.
- Then measure the distance around the largest part of your hips - the widest part of your buttocks. This is your hip circumference.
- The accuracy of waist and hip circumference measurements depends on:
  - The tightness of the measuring tape. The tape should be snug around the body, but not pulled so tight that it is constricting.
  - The correct positioning of the tape around the body (horizontal).
- Complete two measures of both waist and hip circumference and report below as indicated. If the difference between the two is greater than 1cm, please repeat the process a 3rd time.
- Report your measurements in centimeters (cm).

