## Procedure for Distributing mLIFE Study Kits

The mLIFE Study kits, which include a **Fitbit Versa2**, **Fitbit Aria Air Scale**, and **non-elastic measuring tape**, are distributed to participants who have completed at least the initial survey or **three dietary recalls**. These devices are critical for tracking physical activity, weight,

and conduct the hip and waist circumference measures at each time point.

All devices are bought in bulk and kitting services are hired to receive the orders of the Fitbit devices and tapes and to create and label each kit box. USC Post office provides the shipping services to the participants. Once the shipped to a participant, an email containing the **tracking number** is sent to the participant. A designated study assistant monitors the tracking progress to ensure timely delivery. Upon receipt of the kit, a courtesy **phone call** is scheduled to confirm successful delivery and to ensure the participant understands the setup and usage instructions for the devices. If required, a video call is scheduled to assist with the device setup.

The kits includes a welcome letter which provides step-by-step guidance on creating a **Fitbit account**, syncing devices, and verifying the account. Participants are instructed to sync their devices at least once every 5 days and upload a picture of the scale's display for data verification. Additionally, a training session is scheduled to guide participants through linking their Fitbit account to the mLIFE app, ensuring smooth device usage and data synchronization. All kit distribution is tracked in the study's OneDrive/Retention/Cx\_202\_.

During the courtesy call, the RA reminds the participants of the following:

1. Create a FitBit profile on the website (no app). When linking the profile to the mLife app, permission to access FitBit physical activity data will be asked.
2. Wear Versa 2 on your non-dominant wrist. When not exercising, wear it a finger's width above your wrist bone. During workouts, wear it higher for a better fit. Frequent bending of the wrist during exercises like bike riding or weight lifting could interfere with the heart-rate signal if the watch is lower.
3. Wear the Fitbit device on top of your wrist, ensuring the back is in contact with your skin.
4. Follow the manufacturer's instructions for cleaning and caring for the device.

[figure not shown]
---

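### Participants who finish the baseline survey before three dietary recalls are asked for waist and hip values before the kit with the study tape is released to them

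*Combined protocol and SAP*

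**What the plan says.** All references are to the combined protocol and SAP.

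- **Survey.** "A single survey is requested for completion at each time point". At baseline the rule is: "Set the system to send the initial survey invitation email to the participant immediately after they sign the informed consent form". Within it, "Participants are requested to provide self-reported anthropometric measurements, such as hip and waist circumference and body weight", entered in a measurements section. *Hip and waist circumference* confirms where the data go: if the two readings disagree, the survey asks for a third.
- **Tape.** "A tape measure is sent to the participants for hip and waist circumference measurements". The *Written tips* instruct: "Use the tape provided for the study".
- **Kit.** *Procedure for Distributing mLIFE Study Kits* puts the tape in the same box as the tracker and scale, and says these items are needed to track activity and weight "and conduct the hip and waist circumference measures at each time point". Kits "are distributed to participants who have completed at least the initial survey or" three dietary recalls.
- **Randomization.** The same either/or trigger applies: "Participants are randomly assigned once 50% of the baseline assessments are completed (either the baseline survey or the three dietary recalls". *Prior to training meeting procedures* sends the shipping notice on the day of randomization.
- **Text pointing the other way.** The closing paragraph of *Assessments* says recalls were requested before the survey at every time point. *Orientation Agenda*, item 9, lists anthropometry as a component apart from the survey.
- **Role in the analysis.** *Analysis Plan*, part I, names body circumference among the type 2 diabetes risk factors assessed at baseline, 6 and 12 months. It appears in neither hypothesis.

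**The concern.** For a participant who reaches the kit threshold by completing the survey, the step that releases the tape is the same step that asks for measurements made with it. The baseline value is then blank, estimated, or taken with some other tape, while the 6- and 12-month values can be taken with the study tape.

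Change from baseline for that person either cannot be computed or mixes a change of instrument with a change in body size. At stake are the precision of circumference change and the meaning of the within-arm change that would be reported.

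**Working it through.** The plan gives no figure to reproduce here. The check is one of sequence, followed by a bounded estimate of size.

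**1. The two routes to the kit.**

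| Route | Order of events | Study tape usable at baseline? |
|---|---|---|
| (a) Survey complete before three recalls | consent → survey with waist and hip items → kit released → tape arrives | No, unless the items are left blank or re-entered after delivery |
| (b) Three recalls complete before survey | consent → recalls → kit released → survey | Yes, if the participant waits for delivery; nothing holds the survey until then |

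Route (a) is open by design, because the kit and randomization rules both name the survey as sufficient on its own. Completing it first is also easy. The survey goes out at consent, with reminders at 3 days and again 7 days later, whereas the recalls need three separate unannounced days, one of them at a weekend.

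**2. Is there a return step?** None of the survey, circumference, kit or training sections tells the participant to leave the items blank, to return to them after delivery, or to record which tape was used.

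**3. Was there time for one?** From orientation to the first training session:
- Cohort 1: 16–19 May to 28 June 2022 = 40–43 days.
- Cohort 2: 8–11 May to 5 July 2023 = 55–58 days.

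The time existed; the plan does not use it for this purpose.

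**4. How many?** If *p* is the share on route (a), about 240 × *p* participants are affected. The documents do not give *p*, so the range is 0 to 240. As an illustration only, *p* = 0.5 gives 120.

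**5. Effect on precision, on stated assumptions.**
- *Baseline values unusable, complete-case change.* The standard error is multiplied by 1/√(1 − *m*), where *m* is the share lost:
  - *m* = 0.25: 1/√0.75 = 1.15
  - *m* = 0.50: 1/√0.50 = 1.41
  - *m* = 0.75: 1/√0.25 = 2.00
- *Baseline values kept, taken with another tape.* Assume added error with SD *s* = 1 to 3 cm and a change SD *c* of 5 to 7 cm (neither is in the documents). If every baseline is affected, the multiplier is √(1 + *s*²/*c*²):
  - smallest: √(1 + 1/49) = 1.01
  - largest: √(1 + 9/25) = 1.17
- *Like for like at a share of one half.* Keeping the values gives √(1 + 0.5 × *s*²/*c*²), which runs from √(1 + 0.5/49) = 1.005 to √(1 + 4.5/25) = 1.09. Discarding them gives 1.41.

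**6. Effect on bias.** A systematic difference *d* between tapes shifts the mean within-arm change by *p* × *d* in size. The route is settled by what the participant finishes first, which is also what triggers randomization, so *p* should be the same in both arms in expectation. Under *Randomization Procedure*, allocation is revealed only after baseline assessments are complete. The shift should therefore cancel in the between-arm comparison.

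**The case against.** The strongest reply is that baseline was staged. *Assessments* gives a recalls-first order, under which the kit can ship before the survey. *Orientation Agenda*, item 9, treats anthropometry as its own component with its own tutorial. No section says the measurements part must be filled in for the survey to count as complete. *Training Meeting Agenda*, item 1, admits to training only people who have completed every component, and there were 40 to 58 days in which to do so.

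Part of this stands. Staff may well have collected circumferences after delivery, and what the plan lacks is the step, not the opportunity. But the recalls-first order conflicts with a survey invitation triggered by consent, and an order of requests is not an order of completion. The agenda item describes tutorials, while *Survey* and *Hip and waist circumference* place the data entry in the survey itself. Neither passage closes route (a).

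A reader might go further in three ways that the documents do not support:
- **That many baseline circumferences are affected, or that survey-first was the usual route.** This is plausible, but no count by route is given and the recalls-first statement points the other way.
- **That the treatment comparison is biased.** The route precedes randomization and the values precede the reveal of allocation, so no difference by arm is expected.
- **That values entered before delivery should be set to missing.** On the assumed figures above, that costs more precision than keeping them. The complete-case factors are also an upper guide, because a likelihood-based mixed model of the kind planned for weight need not drop people without a baseline value.

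**Conclusion.** The conflict holds for one defined group: participants who complete the baseline survey before three recalls. For them the survey timing, the study-tape instruction and the kit-release rule cannot all be followed as written. The size of the group is unknown.

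The consequence is modest. It adds noise to a supporting, self-reported outcome and may put an instrument shift into within-person change. If the values are kept, the standard error rises by roughly 1–17% even if everyone is affected, on assumed SDs of 1–3 cm for tape error and 5–7 cm for change. The primary outcome, weight from the study scale, does not depend on the tape.

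The conclusion assumes that completing the survey includes its measurements section. The text implies this but does not say it.

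**What to change.** **Plan text.** Take the waist and hip items out of the consent-triggered baseline survey. Put them in a separate RedCap form, released when the courtesy call confirms kit delivery and required before the training meeting. Delivery tracking, the call and the all-components rule already exist. Reconcile *Orientation Agenda* item 9, the order stated in *Assessments*, *Survey*, *Written tips* and *Procedure for Distributing mLIFE Study Kits* so that they describe one sequence.

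**Data already collected.** Compare the date of each baseline circumference entry with the tracked kit delivery date. Report how many were entered before delivery. Keep those values in the main circumference analysis and run a sensitivity analysis that excludes them.

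**Cost.** One extra form trigger, and possibly a few more missing baseline values from people who do not return to the form. For completed cohorts, one date comparison using data the study already tracks.

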### Hip and waist circumference

A tape measure is sent to the participants for hip and waist circumference measurements. The participant will be instructed to measure waist circumference at the iliac crest, and hip circumference will be measured at the maximum protuberance of the buttocks. Two measurements will be taken and should be within 4mm of one another. If they are not, a third measurement will be requested in the survey/

#### Written tips:

- Stand up straight and breathe out. Use the tape provided for the study.
- Measure the distance around the smallest part of your waist, just above your belly button. This is your waist circumference.
- Then measure the distance around the largest part of your hips - the widest part of your buttocks. This is your hip circumference.
- The accuracy of waist and hip circumference measurements depends on:
  - The tightness of the measuring tape. The tape should be snug around the body, but not pulled so tight that it is constricting.
  - The correct positioning of the tape around the body (horizontal).
- Complete two measures of both waist and hip circumference and report below as indicated. If the difference between the two is greater than 1cm, please repeat the process a 3rd time.
- Report your measurements in centimeters (cm).

## Blood pressure

Participants self-report blood pressure: a recent reading taken at a local pharmacy or at home will be recommended. Measurement should be taken after a five-minute rest period, with a digital blood pressure cuff. A minimum of 2 readings will be taken, and the average of those readings will be reported. If there is a  $>5$  mmHg difference between the first and second readings, additional (one or two) readings will be obtained, and the average of these readings will be used.

The following instructions will be provided to the participants:

*Sit quietly for at least 5 minutes before testing.*

Don't smoke, drink caffeine or alcohol, or exercise within 30 minutes prior to testing.

Empty your bladder.

*Sit up straight in a firm, hard-backed chair that supports your back.*

Don't sit or lie on a sofa or bed.

Place feet flat on the floor with legs uncrossed.

Your arm should be supported on a flat surface, such as the chair arm or a table.

The upper arm should be at heart level.

*Place the cuff on your upper arm above the bend in your elbow.*

See your monitor's instructions for an illustration or ask for a demonstration at your doctor's office.

Don't place the cuff over clothing.

*Take at least two readings and record the average result.*

Take two readings one minute apart.

Record your readings and upload a picture of the device showing the numbers.

